### *Human whole blood culture*

For whole blood stimulation, we will use our published protocol for IL-10 function experiments. Briefly, whole blood will be diluted in a serum-free RPMI media (Sigma) containing 5mM glucose, 50 U/ml penicillin and 50 $\mu$ l/ml streptomycin. Diluted 540 $\mu$ l whole blood will be seeded in 24-well plate (Costar) and stimulated using lipopolysaccharide (LPS, Escherichia coli 055:B5; L6529, Sigma) at 1 or 10 ng/ml with or without recombinant human IL-10. The cultures will be incubated at 37°C in 5% CO2 and supernatants will be collected at six

## Research Protocol

hours for analyses of secreted TNF- $\alpha$  on duplicate samples by enzyme-linked immunosorbent assay - ELISA (Human TNF- $\alpha$  DuoSet, R&D System) according to the manufacturer's instructions. The % maximal stimulation is taken as an index of how well the anti-inflammatory cytokine function to inhibit inflammation. A reduction in the ability of IL-10 to inhibit TNF- $\alpha$  production will be an indicative of "resistance" to their anti-inflammatory action.

### *Flow cytometry*

To examine potential changes in anti-inflammatory signalling pathways in circulating immune cells, the proportion of phosphorylated STAT3 (pSTAT3) positive cells will be measured by flow cytometric analysis. Briefly, whole blood samples and isolated monocytes will be stimulated within exogenous IL-10 for 15 minutes at 37°C in a dose-depended manner (0, 1, 10, 50, 100, 1000 ng/ml), 1ml of Lyse/Fix Buffer (BD Phosflow) will be added for erythrocyte lysis and fixation of the phosphorylated status of intracellular proteins. Next, cells will be permeabilized with 1ml of Perm Buffer (BD Phosflow), washed and stained for 60 minutes at room temperature in the dark with the following fluorophore-labelled monoclonal antibodies: anti-CD4-phycoerythrin (PE)-Cy7 (BD Pharmingen, Franklin Lakes, NJ, USA), anti-STAT3 (py705)-AF488 (BD Phosflow), anti-pAMPK (ab23875, Abcam) anti-CD14 (130-094-364, Miltenyi Biotech) and anti-CD210 (BD Biosciences). Stained cells will be analysed by flow cytometry (Cytoflex S, Beckman Coulter).

### *PBMC isolation*

PBMCs will be isolated by gradient density centrifugation to determine changes in immune cell gene expression in response to the intervention. Briefly, whole blood will be diluted

## Research Protocol

1:1 with warm PBS and layered onto 3 mL of Histopaque-1077 (10771, Sigma) in a sterile 12 mL LeucoSep tube (Greiner Bio-One, Austria) and centrifuged at 800 g for 20 min at room temperature. The enriched PBMC layer will be recovered and washed twice with warm PBS with an additional centrifugation step (300 g for 10 min) after each wash. Isolated PBMCs will be stimulated with IL-10 and/or liposaccharide for ~1 hour and stored at -80°C until transcriptomics analysis.

### *Haematology Analysis of Blood*

Whole blood specimens will be analysed for complete blood count (e.g., total white blood cells, haematocrit, haemoglobin, monocytes, neutrophils) using a haematology analyser (DxH 520, Beckman Coulter) to determine changes in clinically relevant health markers before and after the intervention.

### *Semi-Structured Interviews*

Semi-structured interviews will be conducted in a subset of 10-12 participants to explore barriers and facilitators of the intervention and identify its most effective/ineffective aspects; this will help refine the approach and future intervention delivery.

### *Statistical Analysis*

Descriptive statistics will be calculated and data will be assessed for skewness and normality using Q-Q plots and Shapiro-Wilk tests (non-normal distributions will be log transformed as needed). The primary data analyses will be intention-to-treat. We will define feasibility of the exercise snacks intervention as >70% of participants completing at least 67%

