## PROJECT AIM

To conduct a proof-of-concept randomized trial to determine the feasibility and efficacy of a 12-week technology-enabled exercise snacks intervention for improving CRF in previously inactive adults.

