## Research Protocol

snacks or placebo exercise into their daily routines (details below). Efficacy (i.e., the ability to improve CRF) and feasibility (i.e., rates of uptake and adherence) will be measured before and after the intervention with CRF as the pre-defined primary outcome measure. All pre- and post-intervention testing will be performed at UBC Okanagan (Kelowna, BC) or McMaster University (Hamilton, ON); running the trial at two sites will facilitate recruitment, ensuring we can complete the study within the one-year grant timeline. Co-PIs [name] (UBCO) and [name] (McMaster) have an established history of collaboration – including the two exercise snacks studies providing rationale for this project and a previous multi-site exercise trial.

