## Research Protocol

increases in heart rate and CRF. We selected this as the most appropriate control group in attempts to balance randomization expectations, retention, and ethical considerations compared to a true “hands off” or “no exercise” control.

Technology – Participants will be able to log the timing, duration, and number of exercise snacks completed daily as well as the perceived effort (Borg CR-10 scale) and enjoyment (Exercise Enjoyment Scale) of each snack into the platform. Participants will also be sent weekly self-report adherence surveys via email RedCap link wherein adherence will be assessed by asking participants the total number of snacks completed each week. If participants miss the weekly adherence self-assessment, we will follow-up with an email reminder and (if necessary) a follow-up telephone call to help address any concerns/issues that may have prevented them from completing the weekly assessment. To characterize exercise adherence and track changes in daily physical activity, sedentary time, and sleep patterns, we will provide participants with validated thigh-worn triaxial accelerometers (activPAL4) in line with our previous work. Accelerometer data will be obtained during two, separate 7-day periods (intervention weeks 2 and 11) and extrapolated to the rest of the intervention. As exercise adherence generally diminishes over an intervention, obtaining this data during both early and late stages of the intervention will provide valuable information relating to changes in adherence over the intervention.

Virtual check-ins: To help participants complete their customized movement break plan and to address any potential barriers/challenges that you may encounter of the course of the intervention, we will conduct virtual (phone or zoom) sessions at the 4 and 8 week point of the

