### *Exercise adherence*

## Research Protocol

Self-reported adherence to the prescribed intervention will be determined using the automated weekly REDCap surveys. 9 exercise snacks or placebo exercises per week (equivalent to performing at least 3 per day on at least 3 days of the week) will be considered the minimum prescription. Participants completing 6 or more, 1-5, or 0 exercises will be classified as adherent, partially adherent, or non-adherent, respectively.

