## Research Protocol

(i.e., 6 exercise snacks per week) on at least 9 out of 12 weeks. All quantitative dependent variables will be analyzed using linear mixed-effects models with group and time as fixed effects, participant and study site as random effects, and age and baseline fitness as covariates. The between group treatment effect at 12 weeks with 95% confidence intervals will be the main analyses of interest. Although the study is not powered for detecting sex differences, sex will be included in the model to explore its interaction with the treatment effect. Significance will be set at  $p < 0.05$  and Cohen's d effect sizes will be calculated to estimate the magnitude of between-group differences in pre-post change scores. For qualitative outcomes, an inductive thematic analysis will be conducted on interview transcripts by Co-I [name] to ascertain main barriers and facilitators to acceptability.

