### BACKGROUND AND AIM:

From November 2022 to December 5, 2023, we completed the randomized clinical trial titled “Efficacy of Movement Breaks in Real-World Settings” at two study sites, McMaster University (Mac) and the University of British Columbia (UBC). The purpose of the study was to determine the efficacy of performing movement breaks as either vigorous-intensity “exercise snacks” (ES) or low-intensity mobility-based control activities (CTL) on indices of cardiometabolic health. All movement breaks involved ≤60-second bouts of activity performed periodically throughout the day. Participants in both groups were given access to a web platform that provided individualized notifications to remind them to complete their ES or CTL bouts at least 3 times per day on at least 3 days per week (i.e., minimum prescription of 9 movement breaks per week). Identical scripted counselling at baseline, week 4, and week 8 assisted with individualization and progression of the two movement break prescriptions. Exercise prescription progression and variety were accomplished by altering the exercises in weeks 1-4 (Phase 1), weeks 5-8 (Phase 2), and weeks 9-12 (Phase 3). The primary outcome measure was change from baseline in cardiorespiratory fitness (CRF; assessed via cycling VO2peak test) following the 12-week exercise intervention. Secondary outcomes included changes in basic anthropometric measures (body mass and waist circumference); fasting plasma insulin, glucose, homeostasis model assessment of insulin resistance (HOMA-IR), and inflammatory cytokines; device-measured and self-reported adherence to movement breaks; and enjoyment and perceived exertion following movement breaks. It was hypothesized that a 12-week technology-enabled real-world ES intervention would improve CRF as compared to CTL in previously inactive adults.

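### The protocol's feasibility rule has no corresponding output in the SAP, whose adherence bands measure something different; separately, the SAP's cut-off above 67% excludes the 72 snacks it is said to equal

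*Protocol*

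**What the plan says.** **Protocol.** The Project Aim is "to determine the feasibility and efficacy of a 12-week technology-enabled exercise snacks intervention" for improving fitness. Study Design says that "feasibility (i.e., rates of uptake and adherence) will be measured before and after the intervention", with fitness as the primary outcome. Statistical Analysis gives the decision rule: "We will define feasibility of the exercise snacks intervention as >70% of participants completing at least 67" per cent, glossed as ("i.e., 6 exercise snacks per week) on at least 9 out of 12 weeks". The Exercise adherence section takes 9 per week as the minimum prescription and states: "Participants completing 6 or more, 1-5, or 0 exercises will be classified as adherent, partially adherent, or non-adherent, respectively". The weekly survey obtains its count by "asking participants the total number of snacks completed each week" (Step 5, Technology).

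**SAP.** Background and Aim states: "The purpose of the study was to determine the efficacy of performing movement breaks" on indices of cardiometabolic health. Adherence is a key secondary outcome. Under Secondary outcome measures it is banded as *high* (above 67%), *moderate* (50 to 66%) or *low* (below 50%). The bands refer both to total snacks against 9 per week and to days with at least 3 snacks against 3 days per week. Adherence is then modelled with a linear mixed model, in which the main effect of group is named as the result of most interest. The Sensitivity Analysis section uses *high* adherence to define the per-protocol set and equates it with 6 movement breaks a week, or 72 in total.

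From Background and Aim to the references, the SAP has no feasibility objective, no 70% threshold and no count of compliant weeks.

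**The concern.** The protocol's rule concerns consistency: how many people reach a weekly minimum in most weeks. The SAP's bands concern volume, and its model concerns a difference between arms. An analyst who follows the SAP would not produce the one figure that the protocol chose for judging feasibility. A reader of the results could then take the share with *high* adherence as that figure, although the two can differ in either direction.

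The cut-off raises a second, smaller issue. If *high* means strictly above 67%, it excludes the total of 72 that the SAP gives as its equivalent. Per-protocol membership is then undefined for a participant at exactly the intended boundary.

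**Working it through.** **Inputs.** Minimum prescription: 9 snacks and 3 days per week (Protocol, Exercise adherence; SAP, Secondary outcome measures). Duration: 12 weeks. Planned arm size: 40 (SAP, A Priori Sample Size Considerations).

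**1. The SAP's equivalent of 72.** Prescribed total: 9 × 12 = 108 snacks; prescribed days: 3 × 12 = 36. Six per week gives 6 × 12 = 72, and 72/108 = 6/9 = 66.7%. So 72 reproduces as two-thirds of 108. It does not reproduce as more than 67%:
- 0.67 × 108 = 72.36, so the smallest qualifying total is 73 (67.6%).
- 0.67 × 9 = 6.03, so on a weekly reading the smallest qualifying count is 7.
- 71/108 = 65.7% is *moderate* and 73/108 is *high*; 72 is the only total that falls in no band.

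The protocol's gloss fails the same literal test, because 6 of 9 is not at least 67%.

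**2. SAP bands on 12-week totals against the protocol rule.** In both patterns, snacks are taken 3 per day and nobody stops early.

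| Pattern | Snacks | Days with at least 3 | SAP band | Weeks at 6 or more | Protocol rule |
|---|---|---|---|---|---|
| (a) 9 in 8 weeks, 3 in 4 weeks | 72 + 12 = 84; 84/108 = 77.8% | 24 + 4 = 28; 28/36 = 77.8% | *high* | 8 | not met |
| (b) 6 in 9 weeks, 3 in 3 weeks | 54 + 9 = 63; 63/108 = 58.3% | 18 + 3 = 21; 21/36 = 58.3% | *moderate* | 9 | met |

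So *high* is neither sufficient (a) nor necessary (b), and the day component does not rescue it in either case.

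**3. The day component.** Two snacks a day on 4 days every week gives 8 × 12 = 96 snacks (88.9%) but 0 of 36 days, with all 12 weeks at 6 or more. The SAP does not say how the two measures combine, so this participant's band is undetermined.

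**4. The mixed model.** Its group effect is a difference in mean adherence between arms. It does not estimate the share of the exercise snacks arm that meets a rule.

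**5. What the protocol rule requires.** Above 70% of 40 means at least 29 (29/40 = 72.5%, exact 95% CI 56.1% to 85.4%), since 28/40 is exactly 70.0%.

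**6. Could the gap change the conclusion?** The documents give no weekly adherence data, so this step rests on assumed values: person means Normal with SD 2, weekly counts Normal around them, rounded and cut at 0, no dropout, 10,000 simulated arms of 40.

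| Assumed mean per week | Weekly SD | Total of 72 or more | Protocol rule met |
|---|---|---|---|
| 8 | 1 | 84.4% | 83.3% |
| 8 | 2 | 83.6% | 74.8% |
| 8 | 3 | 82.8% | 65.2% |
| 9 | 1 | 93.4% | 92.7% |
| 9 | 2 | 92.8% | 87.3% |
| 9 | 3 | 92.0% | 79.5% |

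Only one of the six scenarios puts the two shares on opposite sides of 70%.

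**The case against.** The best defence is that nothing has been lost. The rule still stands in the protocol's Statistical Analysis section, weekly counts are collected, feasibility is not the primary outcome, and interviews also address it. On that view the SAP omits one descriptive proportion and contains a rounding slip. Much of this stands: the gap is in the specified analyses, not in the data, and the 67% point is a drafting correction that applies to both documents. It does not remove the problem, because the SAP bands adherence by a different rule and names a different result as the one of interest.

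Four stronger readings are tempting, and the documents do not support them.

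- **That no SAP adherence analysis could ever confirm feasibility.** The SAP lists week as a possible timepoint and reports categorical data as N (%). If bands were tabulated by week, success could be inferred at near-uniform adherence. A participant who fails the rule has at least 4 weeks below 6, so 12 failures need at least 48 weeks that are not *high*. With at most 47 of 40 × 12 = 480 person-weeks not *high* (9.8%), at most 11 fail and at least 29 of 40 pass. But the SAP specifies no such table.
- **That the bands would at least reveal failure.** The smallest total that meets the rule is 6 × 9 = 54, so 12 of 40 below 54 snacks would leave at most 28/40. This works only if *low* is judged on totals. The participant in step 3 of the working could be *low* on days and still meet the rule every week.
- **That the intention-to-treat sentence fixes the feasibility denominator.** In the protocol it covers the primary data analyses, and in the SAP the primary outcome, which is fitness. The denominator for the 70% is not stated.
- **That the simulation shows a wrong conclusion is likely.** Its inputs are assumed, so it shows possibility only.

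**Conclusion.** The concern holds in this form: the protocol sets a numerical rule for one of its two aims, and the SAP text supplied specifies no output that gives the proportion the rule needs. On 12-week totals, the SAP's *high* band can disagree with the rule in both directions; this follows from arithmetic on the documents' own figures. How often it would disagree in this trial cannot be known from the documents.

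The cut-off fault is real but small. It concerns a total of exactly 72, or a week of exactly 6 on a weekly reading, and it affects *high* adherence and the per-protocol set. The primary intention-to-treat comparison of VO2peak is not affected. The point should be corrected before results are reported, but it does not threaten the trial's main conclusion.

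**What to change.** **1. Feasibility output.** Add to the SAP the number and proportion of exercise snacks participants with at least 6 snacks in at least 9 of the 12 weekly surveys, with an exact 95% CI, set against the protocol's threshold of more than 70%. State the denominator and the rule for unreported weeks. A reasonable choice is all participants randomised to exercise snacks, with unreported weeks counted as not met and an observed-weeks version alongside. Counting unreported weeks as not met should be declared an exception to the SAP's rule of analysing data as observed. Because the SAP reports "From November 2022 to December 5, 2023, we completed the randomized clinical trial", date the addition and label these as choices made after completion, not as consequences of the intention-to-treat sentence. Do not present the share with *high* adherence as the feasibility result.

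**2. Cut-off.** In both documents replace 67% by two-thirds: at least 6 per week, or at least 72 of 108 in total. Make the SAP bands contiguous. State whether and how the day component enters the band and the per-protocol set, and from which source. The weekly survey asks only for a total, but platform logs can supply daily counts.

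**Cost.** One SAP paragraph, one table and a wording correction in each document, with no new data. The feasibility figure may turn out less favourable than the *high* share, counting missing weeks as not met is conservative, and rules set after completion carry less weight than prespecified ones.

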## Research Protocol

(i.e., 6 exercise snacks per week) on at least 9 out of 12 weeks. All quantitative dependent variables will be analyzed using linear mixed-effects models with group and time as fixed effects, participant and study site as random effects, and age and baseline fitness as covariates. The between group treatment effect at 12 weeks with 95% confidence intervals will be the main analyses of interest. Although the study is not powered for detecting sex differences, sex will be included in the model to explore its interaction with the treatment effect. Significance will be set at  $p < 0.05$  and Cohen's d effect sizes will be calculated to estimate the magnitude of between-group differences in pre-post change scores. For qualitative outcomes, an inductive thematic analysis will be conducted on interview transcripts by Co-I [name] to ascertain main barriers and facilitators to acceptability.

### BACKGROUND AND AIM:

From November 2022 to December 5, 2023, we completed the randomized clinical trial titled “Efficacy of Movement Breaks in Real-World Settings” at two study sites, McMaster University (Mac) and the University of British Columbia (UBC). The purpose of the study was to determine the efficacy of performing movement breaks as either vigorous-intensity “exercise snacks” (ES) or low-intensity mobility-based control activities (CTL) on indices of cardiometabolic health. All movement breaks involved ≤60-second bouts of activity performed periodically throughout the day. Participants in both groups were given access to a web platform that provided individualized notifications to remind them to complete their ES or CTL bouts at least 3 times per day on at least 3 days per week (i.e., minimum prescription of 9 movement breaks per week). Identical scripted counselling at baseline, week 4, and week 8 assisted with individualization and progression of the two movement break prescriptions. Exercise prescription progression and variety were accomplished by altering the exercises in weeks 1-4 (Phase 1), weeks 5-8 (Phase 2), and weeks 9-12 (Phase 3). The primary outcome measure was change from baseline in cardiorespiratory fitness (CRF; assessed via cycling VO2peak test) following the 12-week exercise intervention. Secondary outcomes included changes in basic anthropometric measures (body mass and waist circumference); fasting plasma insulin, glucose, homeostasis model assessment of insulin resistance (HOMA-IR), and inflammatory cytokines; device-measured and self-reported adherence to movement breaks; and enjoyment and perceived exertion following movement breaks. It was hypothesized that a 12-week technology-enabled real-world ES intervention would improve CRF as compared to CTL in previously inactive adults.

### A PRIORI SAMPLE SIZE CONSIDERATIONS

A sample size of 30 participants per group was deemed sufficient to detect a within-between interaction with a medium effect size (Cohen's  $f=0.25$ ,  $d=0.50$ ) for the primary outcome (CRF) assuming 90% power with a two-tailed  $\alpha$  set at 0.05 (G\*Power v3.1). This effect size equates to ~1 metabolic equivalent (MET) increase in CRF (assuming a mean baseline VO2peak of 30-35 mL/kg/min with a SD of 5-7 mL/kg/min[4-9]). The grant was funded by the Canadian Cancer Society Action Grant special call for interventions designed for primary cancer prevention. A 1-MET increase in CRF was deemed clinically relevant for primary cancer prevention based on epidemiological data showing 10-21% decrease in cancer incidence for each 1 MET increase in CRF[1-2]. To preserve power and account for a 20-30% dropout rate, we aimed to recruit 40 participants per group (80 participants total; equal sex distribution). Randomization was stratified based on study site (i.e., Mac or UBC) and participant sex (i.e., male or female). These calculations were documented in the original grant application (Feb 2021), trial protocol (Oct 6, 2022), and SAP (V1 June 2023).

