## EXPERIMENTAL DESIGN

### *Rationale*

The design of this real-world intervention is a natural extension of our lab-based studies showing improved CRF after exercise snack interventions in previously inactive adults. In one of our studies, participants completed a supervised 6-week intervention involving either three daily bouts of vigorous stair climbing (~20 seconds each) performed 1-4 h apart thrice weekly (n=12; male/female = 3/9, age = 20±2 yrs) or performed no exercise (n=12; male/female = 2/10, age = 19.3±1.6 yrs). CRF measured using the gold standard peak oxygen uptake (VO2peak) test was ~5% higher after the exercise snacks intervention compared to the control group (Cohen's d=0.46). The exercise snacks intervention elicited perceived exertion values corresponding to a "hard" effort (~5/10 on the Borg scale) and mean heart rate responses equating ~85% of the age-predicted maximum^21 while being well-tolerated with 100% adherence. In a subsequent lab-based study, inactive adults (n=12, male/female=5/7, age = 22±4 yrs) performed a 6-week cycling-based exercise snacks intervention involving three daily ~20 second bouts of vigorous exercise 1-4 hours apart on three days per week. Similarly to our first study, CRF was ~4% higher after the intervention compared to baseline (Cohen's d=0.57). Although seemingly modest, the ~0.5 MET CRF gain in these studies is impressive for a young healthy population over a relatively short training period. We anticipate that recruiting inactive middle-aged adults (who are typically less fit than their younger counterparts) and increasing

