## Research Protocol

the dose (e.g., number, duration and/or intervention length) of exercise snacks will elicit even larger gains in CRF (e.g., ~1 MET) that correspond with a greater estimated reduction (>10%) in cancer risk.

In the proposed study, participants will perform 3-4 isolated bouts of vigorous exercise per day (on 3-4 days per week) with the exercise stimulus being increased (either via increased exercise duration, complexity, and/or intensity) progressively over the course of the intervention to ensure continuous improvements in health and fitness. To ensure the intervention is individualized to exercise preferences and physical abilities (e.g., fitness, musculoskeletal issues), adaptable to multiple environments (e.g., home, work), and scalable, we will integrate exercise snacks into the well-established, customizable online platform developed by industry partner Seven Movements. The platform provides participants with targeted motivation, support, and feedback to facilitate strong adherence to the intervention. Our approach is backed by evidence supporting the feasibility and efficacy of technology-based applications for improving home-based exercise adherence in adults. Co-I [name] is an expert in theory-based exercise adherence trials, including studies of vigorous interval training and technology-enabled interventions.

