### Outcomes

| Category                                       | Variable   | Timepoints                    |
|--|--|-------------------------------|
| Anthropomorphic Measures                       | Weight, Waist circumference, body mass index (BMI)   | Baseline, 12 weeks            |
| Blood Pressure                                 | Systolic, Diastolic, Mean Arterial Pressure  | Baseline, 12 weeks            |
| Blood Biochemistry                             | Fasting plasma insulin, fasting plasma glucose, HOMA-IR, fasting plasma cytokines  | Baseline, 12 weeks            |
| Complete Blood Count                           | Total White Blood Cells, Hematocrit, Hemoglobin, Monocytes, Neutrophils  | Baseline, 12 weeks            |
| Exercise Behavior (GLTEQ)                      | Bouts of mild, moderate, and strenuous exercise lasting >15min, weekly leisure-time exercise   | Baseline, 12 weeks            |
| Cardiorespiratory Fitness                      | Cycling? VO 2 peak, max HR, peak RER, peak power output (W)   | Baseline, 12 weeks            |
| Movement Break Adherence (Device-worn)         | Device wear time, average minutes per day of total, light, moderate, vigorous, and moderate-vigorous physical activity per day, average minutes of sedentary time per date, sit-to-stand ratio per day | Baseline, week 2 and, week 11 |
| Movement Break Adherence (Self-report)         | Weekly surveys assessing number of movement breaks completed   | Weekly for 12 weeks           |
| Movement Break Adherence (technology platform) | Number of movement breaks completed within the Seven Movements account   | Recorded for each snack       |
| EES  | Exercise enjoyment
1 (Not at all)
2 (Very light)
3 (Slightly)
4 (Moderately)
5 (Quite a bit)
6 (Very much)
7 (Extremely)  | Following each snack          |
| Borg CR-10 scale                               | Rating of perceived exertion
0 (Rest)
1 (Very, very easy)
2 (Easy)
3 (Moderate)
4 (Somewhat hard)
5 (Hard)
6
7 (Very hard)   | Following each snack          |

|  |                        |  |
|--|------------------------|--|
|  | 8
9
10 (Maximal) |  |
|--|------------------------|--|

**Primary outcome:** The prespecified primary outcome for this trial will be a comparison of the change in VO2peak (mL/kg/min) from baseline to 12 weeks between the movement break intervention groups.

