The primary data analyses will be intention-to-treat. Data will be analyzed by constrained longitudinal data analysis (cLDA) via a linear mixed model with fixed effects for timepoint (i.e., baseline and week 12), the interaction between timepoint and intervention group (i.e., ES or CTL), and stratified allocation factors (sex, study site) as well as random effects for participants to account for the correlation of repeated measures within participants. The between-group treatment (interaction) effect estimate at 12 weeks with 95% confidence intervals will be reported as the main analyses of interest. Significance will be set at  $p<0.05$  and Cohen's d effect sizes will be calculated to estimate the magnitude of between-group differences in pre-post change scores.

The cLDA approach constrains the baseline means to be equal between the treatment groups, which is a reasonable assumption in the context of a randomized clinical trial. No missing data will be imputed as per contemporary guidelines [3]. Model specification will be assessed visually using normal probability plots and residuals vs. fitted values plots. Models will be run using log-transformed outcome variables when departure from model assumptions is observed.

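### The SAP's f = 0.25, d = 0.50 and about 1 MET are not the same effect for the primary contrast, so the stated 90% power for 1 MET does not follow from its inputs

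*SAP*

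**What the plan says.** The SAP, under A Priori Sample Size Considerations, states: "A sample size of 30 participants per group was deemed sufficient to detect a within-between interaction with a medium effect size". It labels that effect f = 0.25 and d = 0.50, with 90% power and two-tailed alpha 0.05 in G*Power. It continues: "This effect size equates to ~1 metabolic equivalent (MET) increase in CRF", assuming a baseline SD of 5–7 mL/kg/min, and adds: "A 1-MET increase in CRF was deemed clinically relevant for primary cancer prevention". The section gives no baseline to week-12 correlation, no SD of change and no G*Power effect-size option. It says that the calculation was also recorded in the grant application, the October 2022 protocol and SAP V1.

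The primary outcome (SAP, Outcomes) is a "comparison of the change in VO2peak (mL/kg/min) from baseline to 12 weeks between the movement break intervention groups". The analysis plan is: "Data will be analyzed by constrained longitudinal data analysis (cLDA) via a linear mixed model". Cohen's d is to be reported for between-group differences in change scores.

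The supplied protocol gives 80 recruits (Participants). Its Rationale reports earlier effects of d = 0.46 against control and d = 0.57 against baseline, about 0.5 MET, and anticipates gains of about 1 MET. It contains no power calculation for this trial.

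**The concern.** The pairing of f = 0.25 with d = 0.50 is the rule f = d/2, which holds for a comparison of two group means. The SAP applies it to a within-between interaction, where it does not hold. The same effect is then translated into about 1 MET, so three different quantities are presented as one.

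The SAP calls 1 MET clinically relevant and attaches 90% power to it. A reader who trusts that would take a non-significant primary result as good evidence against a 1-MET benefit. If the 90% really belongs to a larger effect, that reading is wrong.

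**Working it through.** **Inputs.** From the SAP sample-size section: 30 per group (N = 60), f = 0.25, d = 0.50, two-sided alpha 0.05, SD σ = 5–7 mL/kg/min. From the protocol's background section: 1 MET = 3.5 mL/kg/min. The correlation ρ between baseline and week 12 is not given, so the values 0.5–0.9 below are assumptions shown as a range.

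**1. What f = 0.25 means under the default option.** With two groups and two times, a difference in change δ produces interaction cell effects of ±δ/4, so f = δ/(4σ). Hence f = 0.25 gives δ = 1.0σ = 5–7 mL/kg/min, and 5/3.5 = 1.43 MET to 7/3.5 = 2.00 MET. In terms of cell means:

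- snacks +0.5 SD, control flat: f = 0.125
- snacks +0.5 SD, control −0.5 SD: f = 0.25
- snacks +1.0 SD, control flat: f = 0.25

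So f = 0.25 matches d = 0.50 only as a within-group gain mirrored by an equal fall in controls. The protocol gives no ground for that fall. It expects some benefit in both groups (Protocol section, paragraph on blinding), and the control exercises are meant to leave fitness unchanged (Step 5).

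**2. Reproducing the SAP's figure, default option.** λ = N·m·f²/(1−ρ), with m = 2 and df = 1, N−2.

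- ρ = 0.5: λ = 60 × 2 × 0.0625/0.5 = 15.0, power 96.8%; N = 46 already gives 90%.
- ρ = 0.31: λ = 7.5/0.69 = 10.9, power 90.0%.

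Exactly 90% at N = 60 therefore requires an unstated ρ of about 0.31, and it applies to a 1.0 SD difference.

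**3. The 'as in Cohen' option.** λ = N·f² = 60 × 0.0625 = 3.75, power 47.8%; 90% needs N = 172. This equals a two-sample t-test with d = 0.50 on the change score (86 per group).

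**4. d = 0.50 in baseline SD units.** 0.5 × 5 to 0.5 × 7 = 2.5–3.5 mL/kg/min = 0.71–1.0 MET, which reaches 1 MET only at SD 7. Conversely, 1 MET is 0.70, 0.58 and 0.50 SD at SD 5, 6 and 7, or default f = 0.175, 0.146 and 0.125.

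**5. Power for δ = 3.5 mL/kg/min, n = 30 per group.** Baseline-adjusted variance: (2/n)σ²(1−ρ²), 57 df. With complete data and known covariance the cLDA gives the same variance. Change-score variance: (2/n)·2σ²(1−ρ), 58 df.

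| ρ | Baseline-adjusted, SD 5 / 6 / 7 | Change score, SD 5 / 6 / 7 |
|---|---|---|
| 0.5 | 87 / 73 / 59% | 76 / 60 / 48% |
| 0.7 | 96 / 88 / 76% | 93 / 82 / 69% |
| 0.8 | 99 / 96 / 89% | 99 / 94 / 85% |
| ρ needed for 90% | 0.57 / 0.73 / 0.81 | 0.66 / 0.77 / 0.83 |

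At ρ = 0.9 baseline-adjusted power is at least 99% throughout.

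**6. Internal check.** At ρ = 0.31, the value that returns the SAP's 90% for f = 0.25, power for 1 MET is 62 / 47 / 37% by the same interaction test and 80 / 65 / 52% baseline-adjusted. No SD in the stated range gives 90% for both effects at that correlation. The 0.31 is back-solved; nothing shows that the sponsor used it.

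**7. Effect on interpretation.** At SD 6 and ρ = 0.7 the variance is (2/30) × 36 × 0.51 = 1.224, SE 1.106, and the 95% half-width 2.2. An estimate of 1.5 mL/kg/min would have a CI of about −0.7 to 3.7: not significant, and still compatible with 3.5.

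**The case against.** - **The sample-size sentence can be true as worded.** It says 30 per group was deemed sufficient. Under the default option any correlation of 0.31 or more gives at least 90% for f = 0.25. This stands. The fault lies in the conversion from f to d to MET, which makes the 90% appear to apply to 1 MET.
- **The 'as in Cohen' option is unlikely.** It leads to 172, not 60. That is fair, and the default is the more natural reading. The option matters only because it shows that neither definition rescues the statement.
- **The protocol's earlier studies suggest less variability.** Taking about 0.5 MET (1.75 mL/kg/min) over d = 0.46 or 0.57 implies an SD near 3.8 or 3.1. If these are SDs of change, power for 1 MET is 94% or 99%. This is a good reason not to call the trial underpowered. However, those samples were small and young, the figures are rounded, the type of SD is not stated, and the SAP itself chose 5–7.
- **The planned model also adjusts for sex and site.** If these explained 30% of the variance (an assumption), power at SD 6 would rise from 73% to 79% at ρ = 0.5 and from 88% to 90% at ρ = 0.7. The table is therefore approximate, but the dependence on an unstated correlation remains.
- **The inputs may be recorded elsewhere.** The SAP points to the grant application, an October 2022 protocol and SAP V1. They may hold the option and correlation, so the fix starts there.
- **The trial is complete and the CI is already the main result.** True, and the CI in step 7 would be the same had the conversion been right. What changes is whether a reader is told that a 1-MET effect would very probably have been detected.

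**Conclusion.** The concern holds. For the between-group difference in change, f = 0.25, d = 0.50 and about 1 MET are not one effect, and 90% power for 1 MET cannot be derived from the stated inputs. Under the default option the 90% refers to a difference 1.4 to 2 times 1 MET. Under the alternative option 30 per group falls well short of 90%.

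The result rests on the SAP's own SD range, the protocol's value for 1 MET and G*Power's two definitions of f. It does not establish that the trial was underpowered: power for 1 MET could be above or below 90% depending on the correlation. Nothing about the analysis is invalidated. The consequence is confined to how the primary result, particularly a non-significant one, is read against 1 MET, and that is enough to warrant a correction.

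**What to change.** 1. Retrieve the G*Power option and the correlation used from the grant application or SAP V1, or record that they were not documented. Do not present a back-solved correlation as an a priori assumption.
2. Keep the existing sample-size text as the record and add a dated correction withdrawing the equivalence of f = 0.25 with d = 0.50 and about 1 MET. State the difference in change that the calculation covers under the option found or, if it is unknown, under each option, labelled conditional.
3. In the same note, replace the unconditional 90% with conditional power for 3.5 mL/kg/min at 30 per group under the planned cLDA, over SD 5–7 and a range of correlations.
4. Optionally, say that the planned 95% CI will be read against 3.5 mL/kg/min.

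The cost is a check of earlier documents and a short note. N, model, alpha and estimand stay as they are; the stated power becomes conditional and possibly less favourable.
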